1 PROTOCOL SUMMARY

1.1 SYNOPSIS

Title:	TRC-PAD Program: In-Clinic Trial-Ready Cohort (TRC)
Study Description:	Development of a large, well-characterized, biomarker-confirmed, trial-ready cohort to facilitate rapid enrollment into AD preclinical/prodromal trials utilizing feeder registries into the APT Webstudy and subsequent referral to in-clinic evaluation and biomarker confirmation. Participants with known biomarker status may have direct referral to the trial-ready cohort.
Objectives:	1. To build an efficient and sustainable recruitment system in order to enroll an initial TRC-PAD Cohort. 2. To optimize an innovative, adaptive risk algorithm to efficiently identify the most appropriate trial participants. 3. To develop and validate web-based cognitive and functional outcome measures for future clinical trials.
Study Population:	At least 2,000 (1,000 preclinical + 1,000 prodromal AD) trial-ready individuals aged 50-85
Description of Sites:	Approximately 60 AD clinical trials sites
Description of Study	No intervention
Intervention:	
Study Duration:	5 years
Participant Duration:	5 years

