3 OBJECTIVES AND ENDPOINTS

Aim 1: To build an efficient and sustainable recruitment system in order to enroll and retain an initial TRC-PAD Cohort. This approach will markedly accelerate recruitment timelines, shorten time to site activation for trials, and reduce unexplained variance in pre-trial cognitive testing, as compared to current recruitment approaches.

Aim 2: To optimize an innovative, adaptive risk algorithm to efficiently identify the most appropriate trial participants. Once optimized, this algorithm will be able to select amyloid positive individuals (and eventually tau and other neurodegenerative biomarkers) with >75% accuracy, greatly reducing future costly biomarker screen fails.

Aim 3: To develop and validate web-based cognitive and functional outcome measures for future clinical trials. Baseline and longitudinal cognitive performance (including lack of practice effect on repeated web-based cognitive tests), decline on performance based functional measures, and a combination of self- and study-partner report will predict and subsequently track with in-person measures of cognitive (PACC) and functional (CDR-SB) decline.

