Analysis Plan: The use of adaptive approaches to participant selection, data capture and data monitoring will continually optimize the approach. At the end of the five years, formal tests of hypotheses will be conducted to assess the success of the web-based mechanisms by quantitative and qualitative analysis, in particular comparing timelines, cost, screen failure rates and the measured change and variance in cognitive scores to those in preclinical and prodromal studies for which similar data can be obtained. Two-sided, one-sample tests of means (recruitment timelines and time to site activation) or variances (variance in cognitive testing) or corresponding resampling techniques will be used to detect differences between the TRC-PAD sample and comparator data.

Power Analysis: Power analyses for these hypotheses were done using a two-sided, one-sample t-test for means and a one-sample test of variance using the software PASS. A reduction of 10% in mean recruitment timeline, mean time to site activation and unexplained variance in cognitive testing is considered scientifically meaningful. While the sample size selected was based on the need for a Cohort sufficiently large to support an efficacy trial, we have examined the power of this sample to test our hypotheses. 1. A sample size of 2000 participants achieves 90% power to detect a change as little as 3 days (3%) in recruitment timelines and time to site activation for trials,

assuming current estimates of 120+/-40 days respectively. 2 Estimates of baseline variability from completed AD trials range between 4.5 and 10 points in ADASCog11 score within a site. A sample size of 2000 participants achieves 90% power to detect a difference of at least 0.4 points (5% change) in unexplained standard deviation of cognitive scores, assuming a type I error rate of 5%. Thus, there is adequate power to detect very small differences and looking at multiple sub-groups of interest would not compromise power.

Statistical Aim 2: Once optimized, this algorithm will be able to select amyloid positive individuals (and eventually tau and other neurodegenerative biomarkers) with >75% accuracy, greatly reducing future costly biomarker screen fails.

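### The 90% power for a 3-day change in time to site activation counts 2,000 participants, but activation times arise per site activation and only about 60 sites are planned

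*Combined protocol and SAP*

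**What the plan says.** Aim 1 claims, among other things, that the programme will "shorten time to site activation for trials" (Section 3). Under Statistical Aim 1 in Section 9, the analysis plan names the tests: "Two-sided, one-sample tests of means (recruitment timelines and time to site activation", with tests of variances for the cognitive scores.

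The power paragraph that follows says "Power analyses for these hypotheses were done using a two-sided, one-sample t-test for means". It sets the target: "A reduction of 10% in mean recruitment timeline, mean time to site activation and unexplained variance in cognitive testing is considered scientifically meaningful". It then states that a sample of "2000 participants achieves 90% power to detect a change as little as 3 days (3%) in recruitment timelines and time to site activation", "assuming current estimates of 120+/-40 days respectively". One mean and one ± value are printed for two metrics. The paragraph ends by claiming "adequate power to detect very small differences and looking at multiple sub-groups of interest would not compromise power".

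On the number of sites, the synopsis (Section 1.1) gives "Approximately 60 AD clinical trials sites". No section gives an expected number of site activations, an SD specific to activation time, or a separate power figure for it.

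**The concern.** The sample size in a one-sample t-test is the number of independent values of the quantity tested. Time to site activation is naturally one value per site, or one per site per trial. A site that is already active and enrols another 30 participants still has the same activation time. The power statement nevertheless uses the participant count for this metric.

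Shorter site activation is one of the three Aim 1 claims, and a formal two-sided test of it is planned. Someone relying on the stated 90% could read a non-significant result as evidence that activation was not shortened, when the test had little chance of detecting a change of the stated size. The closing claim about very small differences and sub-groups carries the same problem further.

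**Working it through.** **Inputs from the documents.** Two-sided one-sample t-test, significance level 0.05, mean 120 days, ± 40 read as the SD, stated n = 2,000, stated change 3 days, meaningful change 10% of 120 = 12 days (all Section 9); about 60 sites (Section 1.1).

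**Assumptions, because the documents give no figure.** Number of activations per site, an activation-specific SD (20 to 50 days tried), and within-site correlation (0 to 0.5 tried).

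**Formula.** Power = P(|T| > t(0.975, n−1)), where T is noncentral t with n−1 degrees of freedom and noncentrality d·√n/SD.

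**Step 1: the plan's own figure.** n = 2,000, d = 3, SD 40: noncentrality = 3 × 44.72/40 = 3.354, power 91.8%. The difference detectable with 90% power is 2.90 days; the normal approximation agrees: (1.960 + 1.282) × 40/√2000 = 2.90. The printed figure therefore reproduces, with 2,000 independent values.

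**Step 2: one activation per site.** n = 60, SD 40:
- 3 days: noncentrality = 3 × 7.746/40 = 0.581, power 8.8%.
- 12 days: noncentrality = 12 × 7.746/40 = 2.324, power 62.8%.
- Detectable with 90% power: 17.0 days (17.0/120 = 14.2%).

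A simulation with 200,000 replicates gave 8.7% and 63.0% for the two powers.

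**Step 3: can other inputs rescue the 3-day claim?** With 60 activations:

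| SD (days) | Power, 3 days | Power, 12 days | Independent activations for 90% power at 3 days |
|---|---|---|---|
| 20 | 20.8% | 99.5% | 469 (469/60 ≈ 8 per site) |
| 30 | 11.9% | 86.2% | 1,053 (≈ 18 per site) |
| 40 | 8.8% | 62.8% | 1,870 (≈ 31 per site) |
| 50 | 7.4% | 44.8% | 2,921 (≈ 49 per site) |

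At SD 40 with more activations, all treated as independent, power for 3 days is 12.9% with 120, 25.4% with 300 and 45.0% with 600. With 60 activations, the SD would have to be about 7 days to give 90%.

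**Step 4: the 12-day target when sites contribute several activations.** Effective n = 60m/(1 + (m−1)ρ), with m activations per site and within-site correlation ρ, SD 40:

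| m | ρ | Effective n | Power, 12 days |
|---|---|---|---|
| 2 | 0 | 120 | 90.3% |
| 2 | 0.3 | 120/1.3 = 92.3 | 81.4% |
| 2 | 0.5 | 120/1.5 = 80 | 75.5% |
| 3 | 0 | 180 | 98.0% |
| 3 | 0.3 | 180/1.6 = 112.5 | 88.4% |
| 3 | 0.5 | 180/2 = 90 | 80.4% |

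**Step 5: sub-groups.** Half the sites with one activation each (n = 30, SD 40): power for 12 days is 35.6%, and 90% power is reached only at 24.5 days (24.5/120 = 20%).

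**The case against.** The documents never define the unit for this metric; it is inferred from the metric's name. Sixty is a number of sites, not of activations, and the aim speaks of trials in the plural, so activations may exceed 60. The SD of 40 is shared with recruitment timelines, and the word 'respectively' hints that a second pair of values was meant. The 9% is thus one scenario. All of that is fair, but none of it rescues the 3-day claim: no section supplies anything near the number of activations it needs.

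The stronger point is that the plan's meaningful change is 12 days, not 3. Two independent activations per site at SD 40, or one per site at an SD a little below 30, would give about 90% power for it. This stands: the test has not been shown to be underpowered for its own target. What has been shown is that power for that target is unstated.

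Section 9 also calls the aims exploratory and promises estimates with confidence intervals, so a wide interval would reveal the imprecision. That reduces the risk of misreading a null result. It does not remove it, because formal hypothesis tests are planned and a power figure is printed for this metric. Finally, the sample size was chosen on other grounds, so enrolment does not depend on this figure.

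**Conclusion.** The concern holds. The 90% power for a 3-day change does not apply to time to site activation. With one activation per site at 60 sites and SD 40 it is about 9%, and it lies between 7% and 21% for SDs from 50 down to 20. Even five independent activations per site at SD 40 would give only 25%.

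Power for the 12-day reduction is not established. With 60 activations it runs from 45% (SD 50) to above 99% (SD 20), and is 63% at the plan's SD of 40. The sub-group assurance is unsupported for this metric.

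The conclusion rests on the activation being the unit of observation, which follows from the meaning of the metric. The individual percentages rest on the assumed counts, SDs and correlations. The recruitment-timeline figure is not challenged here.

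**What to change.** In the Aim 1 power paragraph, take time to site activation out of the 2,000-participant statement. Give it a separate statement that names the site activation as the unit and states the expected number of activations and an SD for that metric. An example, to be filled with the sponsor's own inputs:

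> Assuming 60 site activations and an SD of 40 days, there is 90% power for a 17-day (14%) reduction and 63% power for a 12-day (10%) reduction. With 60 activations, power for 12 days is 86% at SD 30 and 45% at SD 50. With 120 activations, two per site, at SD 40 it is 76% to 90%, for within-site correlation from 0.5 to 0.

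Specify one record per activation in the analysis, with a random effect for site if sites are activated for more than one trial. Restrict the closing sentence on very small differences and sub-groups so that it no longer covers this metric.

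The cost is wording plus the sponsor's estimate of the number of activations and their SD. The stated power becomes less favourable. No extra sites, participants or data are needed.

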9 STATISTICAL CONSIDERATIONS

All statistical analyses will be based on a pre-specified statistical analysis plan (SAP). This plan will be informed by preliminary data analysis done mid-way during the study to identify the presence of potential sources of bias, including but not limited to the distribution and nature of the data, confounding effects, and amount and type of missing data. Each metric of interest will be initially assessed descriptively. For categorical data, we will use rates as the outcome measures, excluding the missing and unknown cases. For continuous data, parametric (one-sample t-test), non-parametric (Wilcoxon signed rank test) or resampling approaches (bootstrap or jackknife techniques) will be used, as appropriate. Comparisons between metrics from recent, current-technology trials and the TRC-PAD metrics will be made using 95% confidence intervals. A p-value of 0.05 will be used to conclude significant differences between the two study groups. For comparisons of metrics across different sub-groups of interest, t-tests, chi-square tests or resampling techniques will be used, as appropriate for the type (continuous, categorical) and distribution (normal, non-normal) of the data. Regression models (generalized linear models or generalized linear mixed models), as appropriate, will be used to examine associations of covariates of interest with the TRC-PAD metrics.

All statistical analyses will be conducted at the end of the grant cycle with all available data at the point of data cut-off date. Due to the exploratory nature of these aims, no adjustments will be made for multiple comparisons. However, data will be reported as point estimates and confidence intervals to provide the magnitude and variability around each of the estimates. All analyses will utilize R (www.r-project.org).

Statistical Aim 1: This approach will markedly accelerate recruitment timelines, shorten time to site activation for trials, and reduce unexplained variance in cognitive testing.

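### Aim 1 sets its cognitive target in variance but its power in SD; on the variance scale 2,000 participants only just suffice, so the assurance about sub-groups fails (64% power at n = 1,000)

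*Combined protocol and SAP*

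**What the plan says.** Section 3 words Aim 1 as an intention to "reduce unexplained variance in pre-trial cognitive testing, as compared to current recruitment approaches". Section 9, Statistical Aim 1, then has four relevant statements.

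- Target (Power Analysis): "A reduction of 10% in mean recruitment timeline, mean time to site activation and unexplained variance in cognitive testing is considered scientifically meaningful".
- Test (Analysis Plan): two-sided, one-sample tests, where for cognition "variances (variance in cognitive testing) or corresponding resampling techniques will be used to detect differences" from comparator data.
- Power (Power Analysis): "A sample size of 2000 participants achieves 90% power to detect a difference of at least 0.4 points (5% change) in unexplained standard deviation". The type I error rate is 5%. The planning input is that "Estimates of baseline variability from completed AD trials range between 4.5 and 10 points in ADASCog11 score within a site".
- Conclusion (Power Analysis): "there is adequate power to detect very small differences and looking at multiple sub-groups of interest would not compromise power".

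Section 9 names no Aim 1 sub-groups, sub-group sizes or sub-group power. It describes the aims as exploratory, makes no multiplicity adjustment, and says that "data will be reported as point estimates and confidence intervals".

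**The concern.** Read together, a 5% detectable change against a 10% target suggests a two-fold reserve, and the sentence on sub-groups relies on that reserve. But the 5% is a change in SD and the 10% is a change in variance. Once both are on one scale the reserve disappears.

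This is the plan's only statement about sub-group power for Aim 1. A reader who relies on it could take a non-significant variance result within one disease stage as well-powered evidence of no improvement. On the scale as written, a true 10% reduction would be missed about 36% of the time at n = 1,000.

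**Working it through.** **Inputs.** From Section 9: two-sided one-sample variance test, alpha 0.05, n = 2,000, a 10% variance target, and a detectable change of 0.4 points or 5% of SD. From the Synopsis: 1,000 preclinical plus 1,000 prodromal participants. From Section 5.5: a 20% minority enrolment target, so 0.20 × 2,000 = 400. The 1,000 and 400 are illustrative sub-group sizes that I infer from these targets; 500 and 250 are added only to show the trend.

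**Formula.** With df = n − 1 and r = true variance / reference variance,

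power = P(χ²_df < χ²_0.025 / r) + P(χ²_df > χ²_0.975 / r).

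**Step 1: the plan's own figure.** A 5% SD reduction gives r = 0.95² = 0.9025. At n = 2,000 the lower critical value is 1,876.98, and 1,876.98 / 0.9025 = 2,079.75. The lower-tail probability at that point, plus a negligible upper tail, is 0.898. The stated 90% reproduces.

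**Step 2: one scale.** 1 − 0.9025 = 0.0975. The detectable change is a 9.75% variance reduction, against a 10% target.

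**Step 3: power by sub-group size.**

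| n | Variance −10% (r = 0.90) | Plan's own SD −5% (r = 0.9025) | SD −10% (r = 0.81) |
|---|---|---|---|
| 2,000 | 91.3% | 89.8% | >99.9% |
| 1,000 | 64.3% | 61.9% | 99.7% |
| 500 | 36.8% | 35.2% | 91.1% |
| 400 | 30.3% | 29.0% | 83.6% |
| 250 | 20.3% | 19.4% | 63.0% |
| n for 90% | 1,909 | 2,013 | 483 |

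The supportable sub-group size differs about four-fold between the two readings of the target: 1,909 / 483 = 3.95. On the variance scale, the reduction detectable with 90% power is 9.8% at 2,000, 13.6% at 1,000, 18.7% at 500 and 20.7% at 400.

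**Step 4: timelines, for contrast.** A 10% reduction from 120 days is 12 days. With SD 40, a one-sample t-test reaches 90% power at n = 119 and has 99.7% at n = 250. There is ample reserve against the 10% target when the unit is the participant.

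**Step 5: the points figure.** 0.4 / 0.05 = 8, so 0.4 points is 5% only at an SD of 8. The plan does not state that value, although it lies within the quoted 4.5 to 10. Holding 0.4 points fixed at n = 2,000:

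| SD | 4.5 | 5 | 6 | 7 | 8 | 9 | 10 |
|---|---|---|---|---|---|---|---|
| Power | >99.9% | >99.9% | 99% | 96% | 90% | 82% | 73% |

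This affects only the translation into points. Power for a given relative change does not depend on the SD. ADAS-Cog11 is also not among the assessments in the Schedule of Activities or Section 8.1.7; the in-person measures that the plan names are "in-person measures of cognitive (PACC) and functional (CDR-SB) decline".

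**The case against.** The strongest reply is that the word variance was used loosely. The planning range is given in points, which are SD units, so both numerical inputs to the cognitive calculation are on the SD scale. A 5% detectable change against a 10% target would also match the timeline logic in the same paragraph (3% against 10%). On that reading, power is 99.7% at 1,000 and 91% at 500, and the sentence holds for sub-groups of about 483 or more. This is a possible reading and the documents do not rule it out. But the aim, the target and the named test are all worded as variance. The effect that the plan itself calculates, 5% of SD, also has only 62% power at n = 1,000 whichever target was meant. Even the SD reading fails at n = 250 (63%).

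Other points stand in part:

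- The sub-group sizes are inferred, and only 1,000 has firm support, from the enrolment split.
- Section 9 does not say that sub-groups would be tested one at a time against comparator data; it plans comparisons across sub-groups. That does not help: a two-sided variance-ratio F test of 1,000 against 1,000 at a ratio of 0.90 has about 38% power.
- The full-sample calculation is sound, and 2,000 is a minimum set by the needs of an efficacy trial rather than by these tests.
- The aims are exploratory and will be reported with intervals. This limits the harm but does not make the sentence correct, and the Analysis Plan still promises formal hypothesis tests.

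**Conclusion.** The concern holds. The 90% figure is right; the conclusion drawn from it is not. On the variance scale as written, 2,000 participants give 91% power for the target with almost no reserve (1,909 needed for 90%), and power falls to 64% at 1,000 and 30% at 400. The claim that sub-groups leave power intact is therefore wrong for cognitive variance.

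This rests on reading variance literally, on a two-sided one-sample chi-square test at 0.05 with normally distributed scores, and on sub-groups of the inferred sizes. If the target was meant for the SD, the claim holds down to about 483 participants. In either case the plan must say which scale applies. For mean timelines counted by participant, the sentence is defensible. The point should be corrected, but it does not threaten the design.

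**What to change.** 1. State that the 10% cognitive target is on the variance scale, or correct it to SD if that was meant.
2. Limit the sentence about very small differences and sub-groups to the timeline endpoints counted by participant.
3. For cognitive variance, give power by sub-group size on the stated scale: 91% overall, 64% at 1,000 and 30% at 400 for variance; over 99.9%, 99.7% and 84% for SD. Treat sub-group variance results as estimates with 95% confidence intervals.
4. Express the calculation as a relative change for the cognitive measure that is collected (PACC). Label the ADAS-Cog11 points as a planning proxy, and note that 0.4 points is 5% only at SD 8, with power at n = 2,000 from over 99.9% (SD 4.5) to 73% (SD 10).

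The cost is wording. Neither the sample size nor the analysis changes. On the variance scale, the stated sub-group power becomes less favourable.

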Analysis Plan: Initial amyloid PET results will be compared to historical data from preclinical and prodromal studies for which similar data can be obtained and, for prodromal participants, published data from gantenerumab and avagacestat studies. Standard statistical methods (t-tests for continuous measures and chi-square tests for categorical measures) will be used to compare the participants identified as biomarker positive and biomarker negative. Associations between an indicator of biomarker positivity and each of the potential risk factors will be assessed in a two-staged manner using a generalized linear model with a logit-link function or a generalized linear mixed model for binary data (to account for the measurements over time for an individual participant). Univariate associations deemed to be statistically significant ($p < 0.15$) will be included in a multivariable logistic regression model. Potential confounding and effect-modifying variables will be included in the model as covariates, if necessary. The risk factors and the appropriate functional form of these factors that will be utilized in the model will be clearly stated in the SAP and will be based on the results of the preliminary analysis. An individual participant's predicted risk of biomarker positivity will be calculated using the final multivariable risk prediction model and serve as a risk-algorithm. The performance of this model will be assessed using four measures: the concordance index (c-index) to evaluate the discrimination ability, the calibration slope and calibration in the large to evaluate the model calibration, and decision-curve analysis to assess clinical usefulness. The model will be internally validated using 10-fold cross-validation and bootstrap sampling.

Power Analysis: Power analysis was done using a comparison of the area under a ROC curve (AUC) with a null hypothesis value of 0.75. Assuming a total sample size of 2000 participants and a 60% amyloid expected positivity rate, we have 90% power to detect an AUC of at least 0.80 using a two-sided z-test and a level of significance of 5%.

Statistical Aim 3: Baseline and longitudinal cognitive performance, (including lack of practice effect on repeated web-based cognitive tests), decline on performance based functional measures, and a combination of self- and study-partner report will predict and subsequently track with in-person measures of cognitive (PACC) and functional (CDR-SB) decline.

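### Aim 2 does not require predictor selection to be repeated within each fold and bootstrap sample; followed literally, the validated c-index is optimistic by an amount that depends on an unstated number of candidates

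*Combined protocol and SAP*

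**What the plan says.** Section 9, Statistical Aim 2, Analysis Plan, describes these steps:

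- Each potential risk factor is tested for association with biomarker positivity, and "Univariate associations deemed to be statistically significant ($p < 0.15$) will be included in a multivariable logistic regression model". Confounders and effect modifiers are added where judged necessary.
- The risk factors and their functional form "will be clearly stated in the SAP and will be based on the results of the preliminary analysis". The opening of Section 9 places that preliminary analysis midway through the study.
- "An individual participant's predicted risk of biomarker positivity will be calculated using the final multivariable risk prediction model and serve as a risk-algorithm".
- Performance is judged by four measures: "the concordance index (c-index) to evaluate the discrimination ability", calibration slope, calibration in the large, and decision-curve analysis.
- "The model will be internally validated using 10-fold cross-validation and bootstrap sampling".

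The opening of Section 9 adds: "All statistical analyses will be conducted at the end of the grant cycle with all available data at the point of data cut-off date". The Aim 2 power analysis compares an AUC with a "null hypothesis value of 0.75".

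The text does not say whether selection is repeated inside the resampling, whether the apparent or the corrected c-index is reported, or how many candidates there are. Section 2.2 names only domains (demographic, medical, lifestyle and genetic factors, web-based cognitive tests, symptom questionnaires). No set of participants is held out from the preliminary analysis.

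**The concern.** Cross-validation gives an honest estimate only if the held-out fold played no part in building the model. A noise variable passes the p < 0.15 screen because it happens to be associated with positivity in these participants. If the screen was run before the folds were formed, the same chance association is present in each held-out fold and counts as predictive ability. A bootstrap that refits only the selected predictors has the same fault.

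The preliminary analysis is a second route. Risk factors and functional forms chosen on mid-study data are later validated on all available data, which include those same participants.

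At stake is the Aim 2 conclusion. If true discrimination is near 0.75, an upward bias can make a model that does not exceed the benchmark appear to do so. The calibration slope is flattered in the same way.

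**Working it through.** **1. The plan's own figure, and the standard error.** The inputs from the Aim 2 power analysis are "Assuming a total sample size of 2000 participants and a 60% amyloid expected positivity rate", null AUC 0.75, alternative 0.80, two-sided 5%. This gives n1 = 0.6 × 2,000 = 1,200 positive and n0 = 800 negative. The Hanley–McNeil variance is

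[A(1−A) + (n1−1)(Q1−A²) + (n0−1)(Q2−A²)] / (n1·n0), with Q1 = A/(2−A) and Q2 = 2A²/(1+A).

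- A = 0.75: (0.1875 + 1,199 × 0.0375 + 799 × 0.0804)/960,000, so SE = 0.0107.
- A = 0.80: (0.16 + 1,199 × 0.0267 + 799 × 0.0711)/960,000, so SE = 0.0096.
- Power = Φ[(0.05 − 1.96 × 0.0107)/0.0096] = Φ(3.0), about 99.9%.

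The stated 90% is not reproduced; a binormal variance gives 99.4%. The stated figure is conservative and is a separate matter. What is needed here is the SE of about 0.01, the yardstick for the bias.

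**2. How much noise the screen admits (assumed candidate numbers).** About 15% of null candidates pass. With 5 real and 95 null candidates, the expected number selected is 5 + 0.15 × 95 = 19.25; the simulation selected 19.3 on average.

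**3. Simulation.** There were 2,000 participants, 60% positive, independent candidates and 60 replicates per setting (Monte Carlo error about 0.0015). Fixed means the screen is run once on all data and the selected model then goes through 10-fold cross-validation. Repeated means the screen is rerun in each fold. New data means 20,000 fresh subjects. The rows are for a nominal AUC of 0.75.

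| Candidates (real + null) | Fixed CV | Repeated CV | New data | Fixed − new | In SE |
|---|---|---|---|---|---|
| 10 (5+5) | 0.7485 | 0.7476 | 0.7488 | −0.0003 | −0.03 |
| 20 (5+15) | 0.7494 | 0.7463 | 0.7478 | 0.0016 | 0.15 |
| 30 (8+22) | 0.7510 | 0.7461 | 0.7448 | 0.0061 | 0.57 |
| 30 (10+20) | 0.7483 | 0.7444 | 0.7450 | 0.0032 | 0.30 |
| 50 (5+45) | 0.7506 | 0.7416 | 0.7440 | 0.0066 | 0.61 |
| 100 (5+95) | 0.7550 | 0.7358 | 0.7357 | 0.0193 | 1.81 |
| 200 (5+195) | 0.7601 | 0.7237 | 0.7251 | 0.0349 | 3.27 |

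At a nominal AUC of 0.80 the bias is 0.45 SE with 30 candidates, 0.50 with 50, 1.48 with 100 and 2.70 with 200. A separate simulation with six real predictors gives (0.7470 − 0.7397)/0.0107 = 0.7 SE with 40 candidates and (0.7487 − 0.7302)/0.0107 = 1.7 SE with 100.

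**4. Bootstrap.** With 100 candidates and nominal AUC 0.75, the bootstrap-corrected c-index with selection held fixed is 0.755, the same as fixed cross-validation, against 0.736 in new data. With the screen repeated it is 0.730, slightly pessimistic.

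**5. Correlated candidates.** Fixed minus repeated cross-validation with 20, 40 and 100 candidates was 0.003, 0.007 and 0.017 when independent, and 0.001, 0.004 and 0.011 when correlated. The last is 0.011/0.0107, about 1.0 SE. With blocks of five correlated at 0.5, another run gave 0.008 with 100 candidates and 0.002 or less with 30 to 50.

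**6. Calibration slope.** In a 40-replicate run with 100 independent candidates, the fixed-selection slope was 0.93 against 0.86 in new data.

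**7. Effect on a test against 0.75.** If the true AUC is 0.75 and the estimate is biased upward by k SE, the upper-tail error is 1 − Φ(1.96 − k): 2.5% at k = 0, 7.2% at 0.5, 8.7% at 0.6 and 43.6% at 1.8.

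**The case against.** The strongest reply is that Section 9 is silent rather than wrong. It does not say that selection stays outside the resampling, and both planned methods would handle selection properly if the screen were repeated in them. That is correct, and the finding is conditional for that reason. But the order of the text, from screen to final model to validation of that model, leads an analyst following it literally to the biased version.

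A reader might infer that predictors are definitely screened once on the whole data set. The documents do not say so. Part of the choice is to be made from the mid-study analysis, and participants recruited afterwards would not have influenced it. The optimism from that route is then smaller than in a full-data screen; it was not estimated.

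A reader might also take two standard errors as the expected or greatest bias. Neither is supported. Reaching about two takes roughly 100 to 140 independent, mostly null candidates; with 10 to 30 the bias is small, and with 200 it exceeds two.

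Third, one might infer that the inflated figure would misdirect referrals. Section 2.2 describes an algorithm updated iteratively during the study, whereas this analysis comes at the end of the grant cycle, and no passage makes referral depend on the final c-index. Nesting the selection changes the performance estimate, not the model fitted to all the data.

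Finally, Section 9 calls the aims exploratory, and a true AUC of 0.80 lies 0.05/0.0107 = 4.7 SE above 0.75, so the conclusion would then be safe. This limits the consequence to true performance near the benchmark, but the reported estimate is still biased.

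**Conclusion.** The concern holds as a conditional one. The plan does not require the data-driven selection steps to sit inside the cross-validation and bootstrap. If they do not, the c-index compared with 0.75 is optimistic. At 2,000 participants with independent candidates, the optimism is roughly 0 to 0.6 SE with 10 to 30 candidates, 0.5 to 0.7 with 40 to 50, and 1.5 to 1.8 with 100; one SE is about 0.01 on the c-index scale. Correlation among candidates, likely for cognitive tests and questionnaires, reduces it. A smaller sample increases it: with 1,000 participants it is 0.65 SE with 30 candidates and 1.3 SE with 50, where one SE is 0.015.

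The size rests on assumptions the documents cannot settle: the number of candidates, five to ten real predictors with the rest null, and a screen on the full data. The direction rests only on selection being left outside the resampling.

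**What to change.** In the SAP:

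1. List the candidate predictors, with the functional forms and covariates under consideration, and state their number.
2. State that the p < 0.15 screen and every other data-driven choice are repeated within each cross-validation fold and each bootstrap sample.
3. Either count the preliminary-analysis selection as one of those repeated steps, or evaluate the model in participants who were not used for it.
4. Name the optimism-corrected c-index and calibration slope as the reported Aim 2 result.

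A penalised logistic model on the listed candidates, tuned inside the folds, is an optional alternative to the univariate screen; the fix does not depend on it.

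The cost is a few lines of code and SAP text, and a slightly lower reported c-index. In the simulations at nominal AUC 0.75, the fall in cross-validated c-index is 0.001 with 10 candidates, 0.009 with 50 and 0.019 with 100. Evaluating only in participants not used for the preliminary analysis would also reduce the validation sample.
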